## 3. Trial Safety

Invasive monitoring EEG (a.k.a. ECoG) is indicated clinically when presurgical extracranial EEG and video EEG monitoring are inconclusive with regard to the source of seizure activity. ECoG uses subdural and depth electrodes to record electrical activity directly from the brain and clarify any inconsistencies presented by less invasive EEG results. Placement of subdural electrode grids and/or depth electrodes are determined solely on clinical grounds. There is no additional imaging (EEG, MRI, TMS) and/or ECoG electrode placement that are above and beyond the standard of care that the patient would receive if not participating in the research.

Peri-operative considerations related to the clinical procedures (i.e., not related to the research protocol) include:

- All patients admitted for invasive monitoring EEG stay in the ICU at the UW Hospital.
- Patients receive postoperative CT scans to make sure there is no bleeding.

- Patients are on antibiotics to prevent infection
- All patients monitored closely by nursing with serial neurological exams and dressing inspections to look for CSF leak.
- All patients are routinely seen by Neurology and neurosurgical staff.
- Nursing staff and EMU technologists are present 24/7 such that they immediately attend to a patient with a seizure so as to prevent any injuries. No member of the research staff will administer any clinical care. Furthermore, there is no additional clinical monitoring done solely for research purposes.
- Patients have IV seizure medication available in case seizures are too long.
- In addition to EEG there is 24 hr video surveillance as well.
- Decisions regarding resective surgery are made in case conference by consensus while patient is still in hospital.
- Acquired clinical EEG data are saved on hospital servers.

- Although all key personnel involved in data collection are required to have CPR certification, this is only a general protection given the vulnerability of the population. Because all testing will take place within the hospital's ICU, medical staff will be called immediately, per hospital procedures, should emergency clinical care be needed.

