Stage 1. Because we do not know, *a priori*, the characteristics of the neural code underlying the representation of stimulus information in working memory, Stage 1 of the analyses will necessarily have an exploratory quality. At a general level, however, we have principled reasons for first applying MVPA to the ECoG data, and, second, as a back-up plan, applying ROC-based analyses of electrode selectivity. The rationale for starting with MVPA is twofold: first, the novel insights derived from [31-33, 60] were made possible by the application of MVPA; second, MVPA is quite simply more compatible than are univariate methods with the near-universally accepted idea that the brain represents information via distributed patterns of neural activity [e.g., 25, 29, 43]. The first step with MVPA will be to train classifiers to discriminate each stimulus with high-gamma values measured at each electrode in the array during the sample presentation epochs, then to feed data from the delay periods to the sample-trained classifiers. Although this train-on-sample-test-on-delay approach has been successful for decoding stimulus information from fMRI and EEG datasets [e.g., 17, 31, 33, 34, 36, 37, 58, 60], it does assume that the neural representation of information being held in working memory will be the same as it is when that information is being perceived and encoded. Therefore, we will also be prepared to employ a hold-one-trial-out cross validation approach, in which MVPA classifiers will be iteratively trained and tested on data from the Delaypost-cue epochs. The duration of an analysis “epoch” and, indeed, the very data that will be used to train MVPA classifiers, cannot be known until we begin working with these data. For example, with fMRI, MVPA cross validation can be performed on a TR-by-TR basis, the highest temporal resolution possible with fMRI [e.g., 17, 33, 34, 36, 37, 58]. With EEG, however, MVPA performance varies with the width of the sliding window within which spectral power is computed [31, 60], presenting a tradeoff of temporal resolution for classifier performance. Furthermore, because ECoG presents such a rich array of measures, we can’t know *a priori* whether MVPA might be most effective when applied to, e.g., broadband power [39], PAC [66], an event-related potential (ERP), or some other measure.

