If we are successful, with MVPA, at decoding the identity of each of the three stimuli in the stimulus set, we will use the top 10% of electrodes contributing to the discrimination of each stimulus for Stage 2 of the analysis. (I.e., we will use the electrodes with the highest loadings in the importance map of the trained classifier corresponding to each stimulus.) Should the MVPA analyses not yield stable results, however, our back-up plan for Stage 1 will be to quantify each electrode’s selectivity for each item in the stimulus set with receiver operating characteristic (ROC)-based analyses. Such analyses have long been used to quantify the selectivity of single neurons recorded with extracellular electrodes, and a very similar approach has been used successfully in studies carried out by investigators from the ECoG consortium from which patients will be recruited for this project. For example, Parvizi and colleagues [51] indexed the selectivity of electrodes located in mid-fusiform gyrus, for faces vs. non-face stimuli, with a “signal-to-noise ratio” analysis of broadband oscillatory signals in the 40-160 Hz range. Voytek et al. [70] found that condition-specific fluctuations in the magnitude of PAC indexed selectivity of PFC electrodes for specific S-R mapping rules. Therefore, we also expect that oscillatory power in the 40-160 Hz range will be effective for deriving robust ROC estimates.

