Stage 2. Having identified stimulus-selective electrodes in Stage 1 of our analyses, Stage 2 will effect the test of the phase-encoded selection hypothesis. Specifically, we will test the hypothesis that UMLs and AMIs will each be maintained in an active state, as manifested by above-baseline high-gamma power, but that the amplitude of this high-gamma power will be markedly higher for AMIs. Furthermore, this differential level of high-gamma power will be explained by the fact that the (pattern of) electrodes representing the AMI will exhibit higher interregional PAC than will the UMI. Because Voytek and colleagues [69] have shown that PAC in posterior regions tends to be anchored in the alpha band (as contrasted with a bias toward theta-paced PAC in frontal cortex), we expect that the attention-related changes in interregional PAC in ITS, mid fusiform gyrus, VO1, and/or STS, may also be concentrated in the alpha band. Assuming that we do find evidence for a phase-encoded selection mechanism in our working memory task, an important question will be to determine the source of the low-frequency oscillation clocking the predicted selection-related increase in interregional PAC. Our *a priori* working hypothesis is that this will be the “posterior alpha” that is prominent in EEG electrodes

over parietal cortex, strongly associated with visual attention (e.g., [50, 59, 67]), and widely assumed to be generated by thalamocortical circuits encompassing the caudal intraparietal sulcus.

One important point highlighted in our research plan is the fact that study [70], on which the data analysis plan of the present protocol was based, is “limited” to four patients, and to 20-30 trials/condition/patient, it nonetheless featured sufficient power to support, for example, trial-by-trial prediction of behavioral RT, and msec-level resolution of the onset of event-related phase-encoding (i.e., of phase-encoded selection).

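### Sub-study B picks a fixed 10% of electrodes per category without a sign rule, electrode-level selectivity test or overlap rule, then tests unattended items only against an undefined baseline

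*Combined protocol and SAP*

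**What the plan says.** Statistical Considerations, Sub-study B, sets out two stages.

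- **Training.** The first step is to "train classifiers to discriminate each stimulus with high-gamma values measured at each electrode in the array during the sample presentation epochs".
- **Condition for going on.** The selection rule opens with "If we are successful, with MVPA, at decoding the identity of each of the three stimuli in the stimulus set". No accuracy criterion is given.
- **Selection.** The plan then states that "we will use the top 10% of electrodes contributing to the discrimination of each stimulus for Stage 2 of the analysis", explained as "the electrodes with the highest loadings in the importance map of the trained classifier corresponding to each stimulus". An ROC measure of each electrode's selectivity is held back for the case that the classifier results are not stable.
- **Use.** Stage 2 tests whether UMIs and AMIs will "each be maintained in an active state, as manifested by above-baseline high-gamma power", with higher power for AMIs. It also predicts that "the (pattern of) electrodes representing the AMI will exhibit higher interregional PAC than will the UMI". Baseline is not defined.

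Three other places bear on this. Section 3 (Trial Safety) of the Data and Safety Monitoring Plan says: "Placement of subdural electrode grids and/or depth electrodes are determined solely on clinical grounds". The channel exclusions under Data Analysis concern noise, ictal spiking and resected sites, not selectivity. The design of Sub-study B shows two of three categories on each trial, with random cueing, so every trial has an attended, an unattended and an irrelevant category. The Stage 2 text does not use the irrelevant one.

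**The concern.** Stage 1 is meant to deliver stimulus-selective electrodes, and Stage 2 treats each set as representing its item. A ranking on contribution to discrimination does not guarantee that. An electrode that prefers faces helps a classifier to say that a stimulus is not a scene, so it carries a negative weight for scene. If size of weight is what counts, it can rank high for scene. An electrode that responds to both faces and scenes can rank high for scene whatever the sign rule.

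On a trial with the face attended and the scene unattended, such electrodes are active because of the face, and Stage 2 would score that activity as the scene's. The study's central question is whether UMIs are held by elevated activity, so this error could produce the positive answer. It would also reduce the AMI-UMI contrast in power, and probably in phase-amplitude coupling. Since coverage is set clinically, equal numbers of selective electrodes per category cannot be assumed.

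**Working it through.** The plan has no power or error figure that depends on this rule, so there is none to reproduce.

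**Inputs from the documents.** 128 research channels (Data collection and processing); 10% per category; three categories; 96 trials (Sub-study B procedure; Statistical Considerations gives a minimum of 40). Each trial has two samples, so 2 × 96 = 192 sample epochs. Quota: 0.10 × 128 = 12.8, about 13 electrodes per category and 3 × 13 = 39 places, however many electrodes are selective.

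**Assumed, because the documents are silent.** Numbers of selective electrodes, their tuning, noise structure, a ridge classifier on sample epochs, an AMI effect of 1 SD (0.3 SD as a weaker case), and true UMI activity of zero. A false finding is a UMI-set mean above baseline with z > 1.96, nominal upper-tail rate 2.5%.

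**Mechanism.** Apparent UMI activity = share of the UMI set driven by the attended category × AMI effect. In a smaller example (100 electrodes, 10 per set; 10 face-, 2 scene- and 2 word-preferring), ranking without regard to sign put 29-46% face electrodes in the scene set. Apparent scene activity was therefore 29-46% of the AMI effect. If the face set were wholly face-tuned, the AMI-UMI difference would fall to between 1 − 0.46 = 0.54 and 1 − 0.29 = 0.71 of its true size.

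**False UMI findings with 128 electrodes, 13 per set:**

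| Loadings | Tuning and coverage | AMI 1 SD | AMI 0.3 SD |
|---|---|---|---|
| Absolute | Single-category, 4-20 selective per category | 93-100% | 22-50% (4-13 selective) |
| Signed | Single-category, equal coverage | 2-6% | – |
| Signed | 2-5 electrodes per pair of categories respond to both | 47-100% | 9-21% |
| Signed | Single-category, 60 face / 4 scene / 4 word | 55-56% | – |
| Signed | Single-category, 20 face / 4 scene / 4 word | 3-4% | – |

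In the absolute-loading rows 23-33% of each set was tuned to another category, yet hold-out decoding accuracy was 0.73-0.99 (chance 0.33). Successful decoding therefore does not screen out the problem.

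**Dilution with signed loadings and single-category tuning.** With 4 selective electrodes in a set of 13, the set mean is about 4/13 = 31% of the true effect. Simulated AMI effects were 30-35% of true size for 4/4/4 and 10/2/2 selective electrodes.

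**Candidate repairs:**

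- Removing shared electrodes only: still 71-99% false findings when some electrodes respond to two categories.
- Electrode-level selectivity with one category per electrode: 0-5% with single- or dual-category tuning, and the AMI effect is restored. With graded tuning (a 30% response to non-preferred categories), still 99-100%.
- Contrast of the UMI set with the irrelevant-category set: 0-7% in every scenario with the quota kept, and 2-8% under graded tuning after the selectivity rule. Leakage from the attended category is equal on average in both sets when cueing is balanced.

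**The case against.** The strongest reply is that highest loadings, read literally, means signed loadings. A face electrode with a negative scene weight then ranks last, and with single-category tuning there is essentially no leak unless coverage is extremely unequal. That stands. The plan does not state the sign, however, and signed ranking does not protect against electrodes that respond to two categories.

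A reader might infer that the quota itself creates false UMI activity. The documents and the calculations do not support that. With absolute loadings the leak occurs even with 20 selective electrodes per category, more than the quota of 13. With signed loadings and single-category tuning at equal coverage, an unfilled quota adds inert electrodes, which dilute the effect and do not imitate UMI activity.

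A further reply is that the plan calls Stage 1 exploratory and holds ROC analysis in reserve. But the selection rule is stated definitely, its output feeds the Stage 2 test, and ROC is used only if the classifier results are unstable. In the simulations decoding succeeded and the bias remained.

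It is also fair to say that the undefined baseline is as much the weak point as the selection rule: contrasting UMI with the irrelevant category removes most false findings even with the quota kept. That contrast does not undo the dilution or the shrunken AMI-UMI difference, so both parts need attention.

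**Conclusion.** The concern holds in a conditional form. As written, the plan permits electrodes driven by the attended item to be counted as the unattended item's. This biases the UMI test towards a positive result and the AMI-UMI difference towards zero, if absolute loadings are used or if some electrodes respond to more than one category. With signed loadings and single-category tuning, the expected fault is dilution where fewer than 10% of electrodes prefer a category. A leak then needs very unequal coverage, as in the 60/4/4 case.

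The direction follows from the text. The percentages do not: they depend on assumed electrode counts, tuning, noise and effect sizes, and they fall markedly at an AMI effect of 0.3 SD. It would be wrong to conclude that the study will report false UMI activity at these rates. It would equally be wrong to think that a selectivity rule alone cures the problem, since graded tuning defeats it. The point should be settled in the analysis plan before Stage 2 is run.

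**What to change.** Amend Sub-study B, Stages 1 and 2, as follows.

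1. Rank by signed (positive) loading. Admit an electrode to a category only if its own sample-epoch response to that category exceeds its response to each of the other two, using the ROC measure already planned, corrected over electrodes within patient. Assign each electrode to one preferred category. Leave a category out of Stage 2 in a patient with no qualifying electrode.
2. Define the baseline. In addition to it, make the test of UMI activity a contrast of the UMI set with the irrelevant-category set on the same trials. This is needed because step 1 leaves bias when electrodes respond partly to non-preferred categories.

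The cost is wording and analysis time; no new data or patient burden. The downside is that some patient-by-category sets will be small or empty. If one category is left out, the same-trial contrast is possible only where that category is the attended one: with balanced cueing a third of trials, 96/3 = 32. Under graded tuning the AMI-UMI difference also stays understated (with a 30% response to non-preferred categories and UMI activity zero, 1 − 0.30 = 0.70 of its true size), which should be said when it is reported.

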The present protocol is motivated by the fact that the work summarized in the Background and Significance section point to two possibilities: a) It may truly be the case that UMIs are not represented by elevated neuronal activity; or, alternatively, b) UMIs are represented by elevated activity that occurs at too fine-grained a scale to be detected with noninvasive imaging methods. Adjudicating between these two possibilities will require an invasive technique that allows for recording neural signals that relate directly to the “elevated activity” that is at the heart of this question. Thus, to continue to make progress on the core question of the neural bases of stimulus representation in working memory, this Revision Application has been prepared to propose pursuing the following “supplement to Aim 1”:

The Specific Aim of this project is to test the hypothesis, with electrocorticography (ECoG) recorded from neurosurgical patients, that unattended memory items (UMIs) are represented in phase angle-segregated patterns of activity in the high-gamma band (80-150 Hz), and that attentional prioritization within working memory is implemented via a mechanism of phase-encoded selection.

This novel hypothesis derives from a recent discovery, with ECoG, from patients performing a task that required the simultaneous maintenance of multiple stimulus-response (S-R) mapping rules: Different rules were found to be represented in prefrontal cortex (PFC) in patterns of high-gamma activity centered on different phase angles of the underlying theta oscillation, and selection among these rules was implemented by dynamic shifts in the phase angle of theta-band coherence between the PFC (where the rules were stored) and M1 (where they were implemented) [70]. Here, we are proposing that analogous mechanisms of phase-segregated representation and phase-encoded selection may also govern the attentional prioritization of one from among multiple items held in working memory.

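### Stage 2 of Sub-study B is called the test of phase-encoded selection, but its stated contrasts compare only magnitudes, so a positive result would not establish the Aim's phase claims

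*Combined protocol and SAP*

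**What the plan says.** **The Aim.** Specific Aims/Study Objectives, repeated in the Summary of the Protocol within the Data and Safety Monitoring Plan, proposes that UMIs "are represented in phase angle-segregated patterns of activity in the high-gamma band (80-150 Hz") and that prioritization works through phase-encoded selection. The same section explains the idea through the model ECoG study (reference 70). There, different rules sat at different phase angles of a theta oscillation, and "selection among these rules was implemented by dynamic shifts in the phase angle of theta-band coherence" between prefrontal and motor cortex.

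**The test.** Statistical Considerations, Sub-study B, says that "Stage 2 will effect the test of the phase-encoded selection hypothesis" and then lists what will be tested:

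- AMIs and UMIs are each "maintained in an active state, as manifested by above-baseline high-gamma power".
- High-gamma amplitude is markedly higher for AMIs.
- The "electrodes representing the AMI will exhibit higher interregional PAC than will the UMI".

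The text continues conditionally. Assuming that "we do find evidence for a phase-encoded selection mechanism in our working memory task", the next question is the source of the slow oscillation behind "the predicted selection-related increase in interregional PAC". Reference 70 is described as the study "on which the data analysis plan of the present protocol was based".

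**The concern.** The hypothesis is about where in the slow cycle each item's activity falls, and whether a cue shifts the phase relation between regions. The stated contrasts ask how large the activity is and how strong the coupling is. These are different estimands. If Stage 2 is run as written and its predictions come out, the natural write-up is that phase-encoded selection was found. The analysis would not have examined the feature that separates this mechanism from a simpler one, in which both items are active at the same phase and the attended item is coupled more strongly. The study exists to follow up null results from noninvasive methods, so a positive claim that the data were never asked to support would be a costly outcome.

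**Working it through.** Stage 2 states no alpha, effect size, SD or power, so there is no plan figure to reproduce.

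**1. Claim against contrast.**

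| Phase claim | Quantity that would show it | Stated in Stage 2? |
|---|---|---|
| Items held at segregated phase angles | Difference in preferred high-gamma phase between the items held | No; power and PAC size only |
| Phase-encoded selection | Cue-related shift in interregional phase angle | No; AMI against UMI PAC size only |

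Stage 1 does not fill the gap. It selects electrodes by classifier or ROC analysis and leaves the measure open (broadband power, PAC, an evoked potential or something else). It names no comparison of angle. Sub-study A uses alpha power and PAC in a different task.

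**2. Separate electrode sets (exact).** Let high-gamma amplitude be a(t) = b + m·cos(φ(t) − φ₀), with φ(t) the low-frequency phase, m the modulation depth and φ₀ the preferred phase. Over whole cycles the mean of a(t)·exp(iφ(t)) is (m/2)·exp(iφ₀). PAC size is the length of this vector, m/2. For m = 0.5 it is 0.25 at φ₀ = 0, 90 and 180 degrees. Rotating one item's phase changes PAC size by 0.

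**3. Shared electrodes (exact, depths assumed).** Selecting the top 10% of electrodes for each stimulus permits overlap. If one electrode carries both items at depths 0.5 and 0.3, separated by angle θ, PAC size is |0.5 + 0.3·exp(iθ)|/2:

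- θ = 0: 0.8/2 = 0.40
- θ = 90 degrees: √(0.25 + 0.09)/2 = 0.29
- θ = 180 degrees: 0.2/2 = 0.10

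Here PAC size does depend on angle, but a low value may mean weak coupling or opposed phases. Size alone cannot say which.

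**4. Illustrative simulation.** From the documents: 2.5 s delay, 1200 Hz sampling, trial counts 40 and 96. Assumed: 10 Hz rhythm, sample noise SD 1.0, between-trial SD 0.3, each count applied per condition, 100 runs, two-sided 5%. For S1 and S3 the AMI and UMI mean levels are 1.5 and 1.2, with depths 0.4 and 0.2. For S2 both items have level 1.3 and depth 0.3. Power and PAC are compared by t test, angle by permutation. Rejection rates at 40 / 96 trials:

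| Scenario | Power | PAC size | Angle |
|---|---|---|---|
| S1: same phase, AMI larger | 100% / 100% | 100% / 100% | 6% / 4% |
| S2: 90 degrees apart, equal size | 4% / 10% | 6% / 4% | 100% / 100% |
| S3: 90 degrees apart, AMI larger | 98% / 100% | 100% / 100% | 100% / 100% |

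The magnitude contrasts give the same positive answer in S1 and S3. In S2 they have nothing to detect, although segregation is complete. The 100% for the angle test is optimistic: noise is independent across 2.5 × 1200 = 3,000 samples per trial, and the angle was tied to role.

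**5. Alignment matters.** Suppose each category keeps its own fixed angle and is AMI and UMI equally often. The AMI-minus-UMI angle difference within a category is then exactly 0, although the items are segregated. An angle test must therefore say whether it expects separation by item, by role or by presentation order.

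**The case against.** **PAC is computed from phase, and the predicted increase could fail.** This stands. A reader might infer that Stage 2 says nothing about the hypothesis. The documents do not support that: a missing PAC increase would count against the proposed mechanism, and UMI power bears on whether unattended items show elevated activity at all. What does not follow is sufficiency.

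**Stage 2 does not carry the whole Aim.** A reader might infer that it is the only test of the Aim. Statistical Considerations instead gives Stage 1 the task of finding the code in which items are represented, so the representation half falls at least partly there. But Stage 1 is described as exploratory and states no angle comparison either.

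**The sentence about finding the mechanism is conditional.** This stands. The plan does not say outright that power and PAC results suffice. It does call Stage 2 the test, and the only marker it then names for the mechanism is a PAC increase.

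**The method may be given elsewhere.** The plan rests on reference 70, and the quality-assurance text of the Data and Safety Monitoring Plan commits the team to the grant application's procedures. Neither was available. A reader might infer that no angle analysis was ever intended; the documents cannot show that. The supportable statement is that none is stated here. The remark on msec-level onset of phase-encoding describes what reference 70 achieved. The heading on data analyses and predicted outcomes has no text in the copy reviewed, and nothing is drawn from that.

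**Conclusion.** The point holds as a mismatch between the claim and the stated contrasts. Stage 2 as written can support the conclusion that both items are active and that the AMI has higher power and stronger coupling. It cannot by itself support phase segregation or phase-encoded selection. On separate electrode sets the PAC contrast carries exactly no information on preferred angle, which follows from the definition of PAC size as a mean vector length. On shared electrodes it is ambiguous. The simulated rates are illustrative and depend on assumed depths, noise and alignment; the conclusion does not need them.

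A reader might also infer that the above-baseline criterion leaves the plan without item-specific evidence for an active UMI. That goes too far. Stage 1 already applies classifiers to delay-period data and seeks to decode each of the three stimuli. Baseline specificity is a secondary matter and not part of this finding.

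**What to change.** Amend Stage 2 in one of two ways.

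**(a) Add the phase tests.** Per patient, and only where coupling exceeds a surrogate distribution:

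- Compare preferred high-gamma phase between the items held, against one common low-frequency reference. State in advance whether separation is expected by item, role or order. Note that a difference between separate electrode sets may be a fixed lag between sites.
- Test for a cue-related shift in interregional phase angle on the same electrodes.
- Use a circular or permutation test for both.

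**(b) Limit the conclusion.** If (a) is not done, or phase cannot be estimated, report that both items were active with higher power and stronger coupling for the AMI (if so found), and claim neither phase segregation nor phase-encoded selection.

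If the grant application already contains a phase-angle test, state it here.

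**Cost.** Plan wording and extra analysis of data already collected. Precision is the limit. With three categories in balance (an assumption, since cuing is random), 96 trials give 96/3 = 32 per role per category and 96/6 = 16 per cue direction per category pair. The 40-trial minimum in Statistical Considerations gives about 13 and 7. A pre-cue check in Delay1pre-cue would be coarse: 0.5 s × 8–13 Hz is 4.0–6.5 alpha cycles. In some patients phase may not be estimable, and (b) would then apply.
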